6.5.1.6 Post-Treatment Glucocorticoid Dosing

Upon completion of the Treatment Period, subjects will maintain the GC regimen and mineralocorticoid regimen (as applicable) established during Part C until the 30-day follow-up visit unless the Investigator determines that the subject's clinical status necessitates a dosing change. After completion of the study, GC therapy will be managed at the discretion of the subject's treating physician.

6.5.2 Prohibited Concomitant Medications

Other investigational drugs are prohibited during the study.

Rosiglitazone is prohibited during the study because it could affect the subject's ACTH levels. Aromatase inhibitors, testosterone, and growth hormones are also prohibited because these medications could affect the subject's total androgen levels. In general, subjects who require ongoing treatment with these medications should not be screened.

Any other medication or supplement that could impact subject safety or confound interpretation of study results is prohibited during the study.

6.5.2.1 Inducers or Inhibitors of CYP3A4

In vitro CYP reaction phenotyping has indicated that tildacerfont is metabolized by CYP3A4. Therefore, drugs that are known to be moderate to strong inducers or inhibitors of CYP3A4 are prohibited. Use of dexamethasone is not permitted during the study (see [Section 6.5.1.3](#)). Subjects will be advised to refrain from consumption of grapefruit, grapefruit juice, or any fruits that are known to be strong CYP3A4 inhibitors from 1 day before the first dose of study drug until after the final dose.

6.5.2.2 Substrates of CYP3A4 and/or BCRP

In vitro drug interaction studies coupled with physiologically based pharmacokinetic (PBPK) modeling have indicated that tildacerfont has the potential to inhibit CYP3A4 and BCRP. Tildacerfont has also demonstrated the potential to induce CYP3A4 (mRNA), but the net effect on CYP3A4 is moderate inhibition. Phase 1 clinical data have also confirmed that tildacerfont is a moderate inhibitor of CYP3A4. Therefore, drugs that are sensitive substrates or narrow-therapeutic-range substrates of CYP3A4 and/or BCRP must be avoided. Sensitive substrates or narrow-therapeutic-range substrates of BCRP that are not also metabolized by CYP3A4 and that can be administered QD in the morning (separated by approximately 10 hours from evening administration of study drug) may be permitted with monitoring for safety.

Sensitive substrates are drugs whose plasma area under the concentration-time curve (AUC) has been shown to increase ≥ 5 -fold when co-administered with a known inhibitor of the enzyme and drugs for which the AUC in poor metabolizers is >5 -fold the AUC in extensive metabolizers. Drugs with narrow therapeutic ranges are those for which even small increases in a subject's exposure to these drugs (potentially induced by the concomitant use of tildacerfont) could lead to serious safety concerns (e.g., torsades de pointes).

Ethinyl estradiol is a CYP3A4 and BCRP substrate, and tildacerfont may increase the level of ethinyl estradiol by <1.25 -fold. With ethinyl estradiol doses ≤ 35 μ g, exposure to ethinyl estradiol is unlikely to reach the threshold associated with increased thromboembolic or cardiovascular risk that is observed with higher-dose ethinyl estradiol formulations. Thus, any hormonal contraception containing ethinyl estradiol used by female subjects must contain ≤ 35 μ g ethinyl estradiol, is permitted only for subjects who would not be considered at high risk for thromboembolic or cardiovascular complications with estrogen use, and must be used simultaneously with a backup method of contraception according to [Section 5.2.5.2](#). Dosing of oral formulations of hormonal contraception containing ethinyl estradiol should be offset by approximately 10 hours from the evening dose of study drug.

[Section 13.1](#) provides a non-exhaustive list of medications that are prohibited because of their potential for metabolic interactions with tildacerfont. This list shows many commonly used medications, including certain antibiotics, antifungal agents (itraconazole, ketoconazole), statins (lovastatin, simvastatin), anti-inflammatory agents (felodipine), migraine remedies (eletriptan), anxiolytics (buspirone, midazolam), and drugs for erectile dysfunction (avanafil, sildenafil, vardenafil). (Many oncology drugs and medications used to treat the hepatitis C virus and HIV are strong inhibitors of CYP3A4 but are not listed simply because individuals with active cancer, hepatitis C, and/or HIV are excluded from this study.) It is critical that each subject's concomitant medications are carefully compared to the list in [Section 13.1](#).

In all cases, if there is a question or concern about a specific medication being used by the subject, it is appropriate to review the usage with the Medical Monitor before enrolling the subject in the study and/or making a change in concomitant medications.

7 STUDY DRUG DISCONTINUATION AND PARTICIPANT WITHDRAWAL

7.1 Study Drug Discontinuation

Subjects may voluntarily discontinue study drug at any time. The Investigator and/or Sponsor may also discontinue a subject's study drug at any time. When feasible, Investigators should discuss any safety concerns with the Medical Monitor as soon as possible to determine whether a subject should continue or discontinue study drug. Study drug will be discontinued in subjects who experience individual treatment-stopping criteria described in this section. The Sponsor and Investigator will make efforts (when possible) to continue to collect data (according to the Schedule of Post-Screening Activities) on subjects who discontinue study drug.

If study drug is discontinued, the Investigator will report the discontinuation to the Medical Monitor, document the date and reason for study drug discontinuation on the appropriate electronic case report

form (eCRF), schedule an early termination visit for the subject (see the Schedule of Post-Screening Activities in [Section 1.3.3](#)), provide or arrange for appropriate follow-up, and document the course of the subject's condition.

7.1.1 Liver Chemistry Stopping Criteria

Liver chemistry stopping criteria defined in [Table 3](#) are designed to ensure subject safety and to evaluate liver event etiology. The Investigator should notify the Sponsor within 24 hours of awareness if any of the criteria defined in [Table 3](#) are met. Further suggested actions, follow-up assessments, and monitoring assessments are provided in [Section 13.2](#). A significant change in liver chemistry that requires increased monitoring but does not necessarily satisfy stopping criteria may still be considered an adverse event of special interest (AESI) (see [Section 8.3.8](#)).

Table 3. Stopping Criteria and Increased Monitoring for Liver Chemistry Elevations

Criteria	Actions	
ALT \geq 5x ULN	Discontinue study drug and notify Sponsor.	
ALT \geq 3x ULN	AND total bilirubin \geq 2x ULN (>35% direct bilirubin) ¹	Discontinue study drug and notify Sponsor. Possible Hy's Law case— report as SAE .
	AND INR >1.5	Discontinue study drug and notify Sponsor. Possible Hy's Law case— report as SAE .
	AND subject has symptoms (new or worsening) believed to be related to liver injury or hypersensitivity ²	Discontinue study drug and notify Sponsor.
	AND total bile acids >3x ULN	Withhold study drug and notify Sponsor. Repeat liver chemistry tests after 1 week, and discuss with Medical Monitor whether to discontinue study drug.
	ALT \geq 3x ULN only	Monitor weekly for 4 weeks while continuing study drug and notify Sponsor (see Section 13.2.2)
	AND cannot be monitored weekly for 4 weeks	Discontinue study drug and notify Sponsor.
	persists for \geq 4 weeks	Discontinue study drug and notify Sponsor.

Abbreviations: ALT, alanine aminotransferase; INR, international normalized ratio; SAE, serious adverse event; ULN, upper limit of normal.

¹ If serum bilirubin fractionation is not immediately available, discontinue study drug if ALT \geq 3x ULN and bilirubin \geq 2x ULN and record the presence/absence of detectable urinary bilirubin on dipstick, which is indicative of direct bilirubin elevations suggesting liver injury.

² Symptoms related to liver injury include fatigue, nausea, vomiting, right upper quadrant pain or tenderness, and jaundice. Symptoms related to hypersensitivity include fever, rash, and eosinophilia.

7.1.2 QT Stopping Criteria

Study drug will be discontinued for a subject if either of the following criteria is met:

- QTcF >500 msec OR uncorrected QT >600 msec
- Change from screening or baseline in QTcF of >60 msec

One repeat ECG should be performed to confirm the accuracy and persistence of an initial result that fulfills the QT stopping criteria.

7.1.3 Suicidality Stopping Criteria

Tildacerfont is considered to be a central nervous system (CNS)-active drug. Some CNS-active drugs may be associated with an increased risk of suicidal ideation in certain populations. Although tildacerfont has not been shown to be associated with an increased risk of suicidal thinking or behavior in past clinical studies, subjects will be monitored for such events during this study using the C-SSRS (see [Section 8.2.6.1](#)).

Individuals who answer “yes” to Question 3, 4, or 5 in the suicidal ideation section of the C-SSRS at screening or Week 6 are not eligible for this study. Any subject who exhibits any Suicidal Behavior or Suicidal Ideation (eg, answers “yes” to Question 3, 4, or 5 in the suicidal ideation section of the C-SSRS) will have study drug immediately discontinued and should be evaluated by a psychiatrist. This safety finding will be considered an AESI if it is not an SAE (eg, requiring hospitalization) (see [Section 8.3.8](#)).

7.1.4 Depression or Anxiety Stopping Criteria

Individuals who score >12 on either the depression or anxiety subscale of the HADS (see [Section 8.2.6.2](#)) at screening or Week 6 are not eligible for this study. Any subject who develops severe depression or anxiety (Common Terminology Criteria for Adverse Events [CTCAE] Grade 3 or higher), as assessed by the Investigator, will require study drug discontinuation and appropriate follow-up. This will be considered an AESI if it is not an SAE (eg, requiring hospitalization) (see [Section 8.3.8](#)).

7.1.5 Adrenal Insufficiency Stopping Criteria

Symptoms of adrenal insufficiency include weakness, tiredness, anorexia, nausea, vomiting, abdominal pain, orthostasis and muscle and joint aches. Weight loss and hypotension (ie, systolic blood pressure <90 mmHg) are also associated with adrenal insufficiency. Hyponatremia, hyperkalemia, hypercalcemia, azotemia, anemia and eosinophilia may accompany adrenal insufficiency. It is important to note that many of these signs, symptoms and laboratory findings are nonspecific and commonly occur in persons without adrenal insufficiency. The Investigator should use their clinical judgment when determining whether the signs, symptoms or laboratory findings are isolated adverse events or are possibly due to adrenal insufficiency.

The Investigator is strongly encouraged to contact the Medical Monitor to review the presentation and discuss the plan for a subject with any potential AE of adrenal insufficiency.

If the Investigator deems the sign(s), symptom(s) and/or laboratory finding(s) to be due to adrenal insufficiency, the AE should be recorded as adrenal insufficiency. The sign(s), symptom(s) and laboratory

findings resulting in the diagnosis of adrenal insufficiency will be collected on a separate Adrenal Insufficiency Adverse Event CRF and should not be recorded on the Adverse Event CRF.

If a subject develops an adrenal insufficiency AE meeting the seriousness criterion ([Section 8.3.2](#)) or the definition of an adrenal crisis ([Table 2](#)), the Investigator should discuss with Medical Monitor. In cases where a clear explanation for the occurrence of adrenal insufficiency or adrenal crisis is identified, discontinuation of the study medication is not necessary. If there is no clear explanation for serious event of adrenal insufficiency, then PI may discuss further steps with medical monitors.

If the subject develops adrenal insufficiency due to undertreatment (as opposed to an acute stressor), the subject's daily GC dose should be increased by 5 mg HCe and should not be reduced again to the GC dose level associated with adrenal insufficiency (per Investigator judgment and discussion with the Medical Monitor). Study drug should not be discontinued but may be interrupted while GC dose adjustment is made.

In the absence of any clear explanation for the subject's acute adrenal insufficiency, the Investigator should discontinue study drug. This will be considered an AESI (see [Section 8.3.8](#)).

Adverse events or other conditions that lead to GC stress dosing should not be reported as AEs of adrenal insufficiency since the stress dosing is done to prevent, not treat, adrenal insufficiency.

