8.3.8 Adverse Events of Special Interest

AESIs must be monitored on an ongoing basis. These events will be reported with narratives, allowing for the collection of additional information, as warranted. The following may be considered AESIs for this study:

- Significant liver chemistry changes that do not satisfy study drug stopping rules (see [Section 7.1.1](#) and [Section 13.2](#)). Cases of Hy's Law should be reported as SAEs.
- Suicidality as indicated by Type 3, 4, or 5 ideation on the C-SSRS (see [Section 7.1.3](#) regarding study drug stopping criteria for suicidality and [Section 8.2.6.1](#) regarding the C-SSRS). This safety finding will be reported as an AESI if it is not considered an SAE (eg, resulting in hospitalization).
- Depression or anxiety that is moderate or severe (CTCAE Grade 2 or higher), as assessed by the Investigator (see [Section 7.1.4](#) regarding study drug stopping criteria for depression or anxiety). This will be reported as an AESI if it is not considered an SAE (eg, resulting in hospitalization).
- Adverse events of adrenal insufficiency will be reported on a separate Adrenal Insufficiency Form. Additionally, symptoms of adrenal insufficiency will be reported as SAE if they necessitate parental GC administration by a health care professional and two of the following criteria are met: hypotensive (systolic blood pressure <100 mmHg); nausea or vomiting; severe fatigue; documented hyponatremia, hyperkalemia, or hypoglycemia. If hospitalization was required or the event of adrenal insufficiency is deemed to be an important medical event, life-threatening, results in a persistent or significant disability/incapacity or death, it should also be reported as an SAE.
 - For SAEs of adrenal insufficiency, records from the office of health care provider, emergency facility or hospital the following information should be obtained as source documents to provide the following information:
 - Was stress dosing employed prior to the adrenal insufficiency event? If yes, what were the GC dose and duration of dosing and the cause for stress dosing prior to seeking medical attention?
 - What type, dose and route of parental GC was administered and the duration of administration?
 - What concomitant medications were administered?
 - What clinical laboratory results are available?
 - What AEs occurred?
 - What was the duration of stay if admitted to the hospital?
 - What was deemed to be the inciting factor leading to adrenal crisis?

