### **9.3.25 Adverse Events**

AEs are those AEs with onset date from the signing of the ICF until the end of the follow up period.

Treatment-emergent adverse events (TEAEs) are defined as any AEs, regardless of relationship to study drug, that have an onset or worsening in severity on or after the first dose of double-blinded study drug (within Treatment Period) until 30 days after the final dose of study drug (safety follow-up visit).

If a subject discontinues study drug but remains in the study, AEs with onset date after 30 days of last dose of study drug until the end of the follow up period will be considered post-treatment adverse events.

Related TEAEs are those reported by investigators as possibly related, probably related, or definitely related to the study drug.

AESIs are events that must be monitored on an ongoing basis as defined in Protocol Section 8.3.8 and identified in the AE eCRF page. The AESIs that are serious AEs (SAEs) will be handled according to guidelines from the National Cancer Institute Common Terminology Criteria for Adverse Events (CTCAE 2017) version 5.0, as described in Protocol Section 8.3.3.1.

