**Table 11 Potentially Clinically Significant Abnormalities by Vital Sign Parameter**

Vital Sign Parameters	PCSA Low	PCSA High
Pulse Rate (bpm)	< 40	> 110
Systolic Blood Pressure (mmHg)	< 85	> 160
Diastolic Blood Pressure (mmHg)	< 45	> 100

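### Adrenal insufficiency is reported on one form while AESIs are counted from another, so non-serious events, including those after a Part C glucocorticoid reduction, may miss the AESI table

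*Protocol*

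**What the plan says.** **Scope.** Protocol 7.1.5 discusses AI with a clear explanation, AI from undertreatment, and acute AI with no clear explanation. AESI status is mentioned only for the last: "the Investigator should discontinue study drug. This will be considered an AESI". Protocol 8.3.8 opens its list with "The following may be considered AESIs for this study" and includes AEs of AI with no condition on cause.

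**Forms.** Protocol 8.3.8 states: "Adverse events of adrenal insufficiency will be reported on a separate Adrenal Insufficiency Form". Protocol 7.1.5 has the event recorded as an AE of adrenal insufficiency without naming the form. It places the supporting signs, symptoms and laboratory findings on a separate AI CRF and says that they "should not be recorded on the Adverse Event CRF". Protocol 8.3.6 puts AESIs on the SAE Report Form.

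**Analysis source.** SAP 9.3.25 takes AESIs "as defined in Protocol Section 8.3.8 and identified in the AE eCRF page". SAP 14.1.2 plans a table of AESIs by system organ class and preferred term. The SAP does not mention the AI form and plans no table specific to AI. AI appears there only in the hospitalisation history (SAP 11.4.2.3).

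**Related wording.** Protocol 7.1.5 describes hypotension associated with AI as "systolic blood pressure <90 mmHg". The 8.3.8 rule for reporting AI as an SAE uses a limit of 100 mmHg.

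**The concern.** Part C lowers background GC in subjects whose A4 is controlled, and AI is a direct hazard of doing so. If the event is reported on one form and the AESI table is built from another, the table depends on how each site reads the protocol. The 1-day AESI notification in Protocol 8.3.5 has the same weakness, because it applies only if the site regards the event as an AESI.

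The likely direction matters more than the size of any single event. Serious AI is captured through SAE reporting. Non-serious AI, which can include AI from undertreatment after a planned GC reduction, has no such backstop. An incomplete AESI table would tend to make the GC-sparing strategy look safer than it was.

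**Working it through.** No figure in the plan bears on this point, so the check compares the texts and follows one event through them.

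| Place | What it directs |
|---|---|
| Protocol 7.1.5 | Diagnosis recorded as an AE, form not named; supporting findings on the AI CRF and off the AE CRF |
| Protocol 8.3.5 | AE eCRF for non-serious AEs that need no immediate report; SAEs and AESIs notified within 1 day |
| Protocol 8.3.6 | AESIs on the SAE Report Form |
| Protocol 8.3.8 | AEs of AI on the separate AI form |
| SAP 9.3.25 | AESIs defined by Protocol 8.3.8, identified on the AE eCRF page |
| SAP 14.1 | AE terms from the eCRFs in general are coded |

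**Step 1. Follow a non-serious AI event after a Part C GC reduction.**
- *The site treats it as an AESI (8.3.8).* The named destinations are the AI form and the SAE Report Form. The AE eCRF sentence in 8.3.5 does not clearly apply, since an AESI needs immediate notification. If nothing is entered on the AE page, the source in SAP 9.3.25 does not contain the event.
- *The site does not treat it as an AESI, because 7.1.5 gives that status only to unexplained acute AI.* The event may reach the AE page through 8.3.5, but without an AESI flag. It then appears among the treatment-emergent AEs and not in the AESI table.
- *The site enters the diagnosis on the AE page and flags it.* The event is counted. Nothing in the AI text requires this.

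**Step 2. Compare with another AESI.** For liver events that meet stopping criteria, Protocol 13.2.1.1 asks for the AE eCRF with an indication that the event is an AESI. That matches SAP 9.3.25. AI has no equivalent instruction.

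**Step 3. Size of one event.** All subjects receive 200 mg in Part C, so the relevant column is pooled. The planned number is 72, and the assumed dropout over the Treatment Period is 15% (Protocol 9.2).
- No dropout: 1/72 = 1.4 percentage points.
- With planned dropout: 72 × 0.85 = 61.2, so about 61 subjects, and 1/61 = 1.6 points.

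The documents give no expected number of AI events or of subjects who will reduce GC, so the total shortfall cannot be estimated.

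**Step 4. Other inconsistencies in the AI text.**
- Hypotension is below 90 mmHg systolic in 7.1.5 and below 100 mmHg in the 8.3.8 SAE rule. A reading of 90 to 99 mmHg meets the second and not the first.
- 7.1.5 refers to Table 2 for the definition of adrenal crisis. The crisis row of Table 2 contains treatment only.
- Within 7.1.5, one paragraph leaves unexplained serious AI to discussion with the medical monitors, while a later one has study drug discontinued for unexplained acute AI.

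**The case against.** The strongest reply is that the plan can be read so that nothing is lost. Protocol 7.1.5 concerns stopping, and its narrower text can sit inside the wider 8.3.8 list, just as 7.1.4 speaks of Grade 3 or higher depression or anxiety while 8.3.8 lists Grade 2 or higher. SAP 9.3.25 adopts the 8.3.8 definition for analysis. The AI diagnosis is still recorded as an AE, and only the supporting findings are kept off the AE CRF. SAP 14.1 codes terms from the eCRFs in general, which does not exclude the AI form, so AI could still appear among treatment-emergent AEs by study part. Serious AI is reported within 24 hours whatever its AESI status.

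Most of this stands, and it rules out several stronger readings:
- A reader might infer that 7.1.5 limits AESI status to unexplained AI, so that every explained event changes status between sections. It does not say so; it is silent on explained AI. Nor does 8.3.8 make AI an AESI without qualification, since its heading is permissive.
- A reader might infer that AI events will disappear from the safety output. The documents show only that they can be left out of the AESI table.
- A reader might count the 85 mmHg systolic limit in SAP Table 11 as a third AI definition. It is a general vital-sign flag, and no AI count is derived from it.
- A reader might size the problem on a randomised arm of 18 (1/18 = 5.6 points). That is the wrong denominator for Part C.

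What the reply does not cure is the specific AESI rule. General coding wording in SAP 14.1 does not put an event into a table whose source is the AE page, and a shared definition does not help if the event or its flag is on a different form.

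**Conclusion.** The mismatch between reporting form and analysis source is real. Followed literally, the protocol and SAP can leave non-serious AI, including AI after a Part C GC reduction, out of the AESI table. The AESI scope for AI is also unsettled between 7.1.5 and 8.3.8.

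One omitted event is worth about 1.4 points in a pooled Part C group of 72, or 1.6 points at the planned dropout. The conclusion assumes that some sites would use the AI form or the SAE Report Form without a flagged entry on the AE page; the documents permit this but do not show how often it would occur. CRF completion instructions outside these documents could narrow the gap. The efficacy analyses are not affected. The blood-pressure mismatch, the missing crisis definition and the conflict within 7.1.5 are genuine but secondary.

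**What to change.** - **Protocol 7.1.5 and 8.3.8:** state one AESI scope for AI in both places, and say expressly whether explained AI is included.
- **Source:** require every AI diagnosis on the AE page with the AESI flag, with the AI form as a supplement. Align 8.3.6 with this, and name both sources in SAP 9.3.25 and 14.1.
- **SAP 14.1:** add one table of AI events by study part and, in Part C, by whether GC had been reduced beforehand.
- **For the sponsor to reconcile:** the two hypotension figures for AI, the reference to a crisis definition that Table 2 does not contain, and the two passages in 7.1.5 on unexplained AI. No view is taken here on which is right.

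The cost is wording in both documents, one consistently applied flag and one extra table. The table uses AE, AI-form and GC-dose records that are already planned, so no new data are needed.
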